#### Subgroup analysis for Asian participants

The sample size of participants of Asian ethnicity at 4% is very limited and prohibitive to conducting meaningful statistical inference. However, there's regulatory interest in quantifying the effect of treatment on the subgroup of Asian participants. Thus, the analysis on change from baseline at Week 10 in ZAN-BPD total score will be evaluated descriptively (by (i) treatment, and by (ii) combined active treatment vs placebo) using standard aggregate measures such as unadjusted mean, median, and quartile ranges.

Furthermore, there is interests in evaluating the subgroup of East Asians which is defined as Japanese participants from sites in Japan. Given the low numbers of participants, descriptive statistics and patient listings will be created for the clinical trial report.

## **7.5 SECONDARY ENDPOINT(S)**

### **7.5.1 Key secondary endpoint(s)**

This section is not applicable as no key secondary endpoint has been specified in the CTP.

### **7.5.2 (Other) Secondary endpoint(s)**

#### Logistic regression analysis

The binary secondary endpoint of ZAN-BPD response (defined as  $\geq 30\%$  ZAN-BPD reduction from baseline at Week 10) will be analyzed through a logistic regression model to obtain an estimate of the population odds ratio (OR) and associated confidence intervals between active arms and placebo. This logistic regression will be adjusted for fixed factors of treatment, baseline ZAN-BPD strata indicator ( $\leq 18$  vs.  $\geq 19$ ), and the continuous covariate of baseline ZAN-BPD total score. The analysis will be performed on the FAS. Adjusted odds ratios

together with 95% confidence intervals will be used to quantify the effect of treatment, comparing all treatments to placebo.

The SAS code for the logistic regression model is as follows:

```
proc logistic data=indata;  
  class trt stratum / param=GLM; /* include (ref="placebo") for trt*/  
  model resp = trt base stratum / link=LOGIT covb;  
  lsmeans trt / cl;  
run;
```

Adjusted odds ratio together with 95% confidence intervals, comparing all treatments to placebo, will be presented.

For *the rest of the secondary endpoints*: (i) change from baseline in DERS-16 total score at Week 10, (ii) change from baseline in STAI-S total score at Week 10, (iii) change from baseline in PHQ-9 total score at Week 10, (iv) change from baseline in CGI-S at Week 10, and (v) change from baseline in PGI-S at Week 10, an MMRM model like that described for the primary endpoint analysis will be used to obtain the adjusted change from baseline at Week 10 for each of the BI active arms versus placebo.

The analysis of standard PK parameters is performed according to (6).

### **7.5.3 Sensitivity analysis of ZAN-BPD response**

#### Additional risk factors to ZAN-BPD response

The binary secondary endpoint of ZAN-BPD response (defined as  $\geq 30\%$  ZAN-BPD reduction from baseline at Week 10) will be analyzed through a logistic regression model as detailed in [Section 7.5.2](#), but with the addition of further potential risk factors to the estimate of the population odds ratio (OR) and associated confidence intervals between active arms and placebo. The logistic regression model for ZAN-BPD response will be repeated (as given in Section 7.5.2) but with the addition of the covariates of stable concomitant psychotherapy (yes/no) and sex (male/female). The analysis will be performed on the FAS. Adjusted odds ratios together with 95% confidence intervals will be used to quantify the effect of treatment, comparing all treatments to placebo. In case zero event is observed in any of the combination of treatment arm and strata, a penalized regression based on the Firth's bias reduction method ([10](#), [11](#)) will be used.

## **7.7 EXTENT OF EXPOSURE**

Extent of exposure will be calculated as the difference between last intake of study drug and the first administration of the study drug plus one day. Descriptive statistics will be provided for number of days of exposure for each treatment arm. Also, cumulative exposure of number and percentage (N, %) of subjects will also be displayed as “< 1 week”, “1 to < 2 weeks”, “2 to <3 weeks”, “3 to <4 weeks”, “4 to <6 weeks”, “6 to <8 weeks”, “8 to <10 weeks”, “10 to <12 weeks”, “12 weeks”, “>12 weeks”, or “missing”.

## **7.8 SAFETY ANALYSIS**

All safety analyses will be performed on the treated set. AEs will be coded based on the most current version of MedDRA. Analysis will be performed as defined in Section 7.2.5 of the CTP.

### **7.8.1 Adverse Events**

The analyses of adverse events will be descriptive in nature. All analyses of AEs will be based on the number of patients with AEs and not on the number of AEs. The reporting and analyses of AEs will follow the BI guideline (12). AEs will be coded with the most current version of MedDRA.

For analysis of AE attributes such as duration, severity, etc. multiple AE occurrence data on the CRF will be collapsed into one AE event if all the following apply:

- All AE attributes are identical (LLT, intensity, action taken, therapy required, seriousness, reason for seriousness, relationship, and outcome).
- The occurrences were time-overlapping or time-adjacent (time-adjacency of 2 occurrences is given if the second occurrence started on the same day or on the day after the end of the first occurrence).

For further details on summarisation of AE data, please refer to ([5](#), [12](#)).

The analysis of AEs will be based on the concept of treatment emergent adverse events, thus, all adverse events occurring between the date of the first administration of trial treatment through the date of the last administration of trial treatment + residual effect period will be assigned to the on-treatment period. Adverse events that occur before first drug intake will be assigned to 'screening', and adverse events that occur within 28 days after the residual effect period will be assigned to 'follow-up'. For details on the treatment definitions, see [Section 6.1](#).

#### Adverse events of special interest (AESIs)

A hepatic injury is defined by the following alterations of hepatic laboratory parameters:

- an elevation of AST and / or ALT  $\geq$  3-fold ULN combined with an elevation of total
  - o bilirubin  $\geq$  2-fold ULN measured in the same blood draw sample; and / or
- marked peak aminotransferase (ALT and / or AST) elevations  $\geq$  10-fold ULN.

Refer to CTP Section 5.2.6.1.4 for details.

#### Other significant AE (according to ICH E3)

According to ICH E3 ([13](#)), AEs classified as "other significant" needs to be reported and will include those non-serious and non-significant AEs with

1. action taken = 'discontinuation' or 'action taken = reduced'; or
2. marked hematological and other lab abnormalities or lead to significant concomitant therapy as identified by the Clinical Monitor / Investigator during medical quality review at TOM.

#### AE summaries

An overall summary of adverse events will be presented. The frequency of patients with adverse events will be summarized by treatment, primary system organ class (SOC) and preferred term (PT) according to MedDRA. The SOC's will be sorted by default alphabetically and PTs will be sorted by frequency within an SOC. Separate tables will be provided for patients with:

- drug-related AEs
- serious AEs
- serious related AEs
- AESIs
- other significant AEs (according to ICH E3)

- AEs leading to death
- AEs leading to discontinuation of trial medication
- AEs occurred with incidence in the preferred term >2%
- AEs occurred with incidence in the preferred term >5%
- AEs occurred during the follow-up period.

#### AEs suggestive of abuse potential

In support of an evaluation of human abuse potential, user-defined AE categories (UDAEC) are defined in [Section 10.5](#). In addition, frequency of subjects with AEs suggestive of abuse potential will be summarized by treatment, UDAEC, and preferred term. A listing of the AEs and a listing of subjects with >100% compliance or unreturned medication kits will also be provided.

#### **7.8.2 Laboratory data**

The analyses of laboratory data will be descriptive in nature and will be based on BI standards [\(14\)](#). Only patients with at least one available on-treatment value will be included in the analysis of an individual laboratory parameter. All individual data will be presented in listings. Study visits will be presented by the Visit labels in [Table 6.7.1](#).

#### **7.8.3 Vital signs**

Only descriptive statistics are planned for this section of the report. In case of multiple measurements including unscheduled visits, the value for the vital sign measurement will be the average of all the measurements for the corresponding visit.

#### **7.8.4 ECG**

12-lead ECG measurements will be assessed as described in the CTP Flow Chart. 12-lead ECG-findings before first intake of trial drug will be considered as baseline condition or as AEs (during the trial) if judged clinically relevant by the investigator and will be analysed as such. No separate listing or analysis of these ECG data will be prepared.

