#### 5.2.4 Electrocardiogram

The 12-lead ECGs will be performed as scheduled in the [Flow Chart](#). Twelve-lead ECGs (I, II, III, aVR, aVL, aVF, V1 – V6) will be recorded using equipment provided by a central ECG vendor. The ECGs will be recorded for at least 10-second duration after the subjects have rested for at least 5 minutes in a supine position and prior to lab sampling. Electrode placement will be performed according to the method of Einthoven/Goldberger (ankles and wrists). At time points indicated in the Flow Chart, single ECGs will be recorded. ECG recordings at planned time points may be repeated for quality reasons like alternating current artefacts, muscle movements and electrode dislocation. In this case the repeated ECG recordings will be used if quality was better.

The investigator or a designee will evaluate whether the ECG is normal or abnormal and whether it is clinically significant, if abnormal. The electronic version of the ECG is regarded as source data. Dated and signed printouts will be stored in the patient's medical file if there is no validated and certified e-medical record for ECG data.

Additional ECGs may be collected by the investigator for safety reasons. Clinically relevant findings noticed at Visit 1 should be reported as baseline conditions. Clinically relevant, abnormal findings noticed after Visit 1 should be reported as AEs and followed up and/or treated locally until the condition returns to normal or becomes stable condition.

All ECGs will be transmitted electronically to the central ECG vendor in order to enable a centralized and independent re-evaluation of all 12-lead ECGs. A centralized and independent re-evaluation will be done.

Central evaluation on an individual ECG level will be performed by the vendor and a report will be provided to the site. Decisions on eligibility for the trial and treatment or further follow-up of any findings are in the responsibility of the investigator.

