A non-flat dose response is established if at least one dose response pattern is statistically significant, rejecting the null hypothesis of a flat dose response relationship over change from baseline to Week 10 in ZAN-BD total score jointly for each of the candidate models with a contrast test controlled for the family-wise type I error rate at one-sided  $\alpha = 10\%$ .

If a non-flat response is established, the statistically significant (i.e., best fitting) model(s) are refitted to the data to generate new estimates for all model parameters. The final model will be obtained via model averaging across the significant models based on Akaike Information Criteria. The target dose(s) can be estimated from each significant model by incorporating information on the minimum clinically relevant effect. Safety will be taken into account in the selection of a target dose(s).

[figure not shown]

Figure 7.2.2.1: 1 Shape of the considered dose response patterns for the MCPMod analysis

If considered necessary and for the purpose of further model refinement, MCPMod might be repeated on the primary endpoint but with an extended set of shapes including the original candidates.

Sensitivity analyses to assess the robustness of the primary analysis outcomes to the assumption of MAR will be described in the TSAP.

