### 7.2.5 Safety analyses

Adverse events will be coded using the Medical Dictionary for Drug Regulatory Activities (MedDRA). Standard BI summary tables and listings will be produced. All adverse events with an onset between start of treatment and end of the period of 28 days after the last dose of trial medication, will be assigned to the on-treatment period for evaluation.

All treated patients will be included in the safety analysis. In general, safety analyses will be descriptive in nature and will be based on BI standards. No hypothesis testing is planned.

Statistical analysis and reporting of adverse events will concentrate on treatment-emergent adverse events, i.e. all adverse events occurring between start of treatment and end of the REP. Adverse events that start before first drug intake and deteriorate under treatment will also be considered as 'treatment-emergent'.

Frequency, severity, and causal relationship of adverse events will be tabulated by system organ class and preferred term after coding according to the current version of the MedDRA at database lock.

Laboratory data will be analyzed both quantitatively as well as qualitatively. The latter will be done via comparison of laboratory data to their reference ranges. Values outside the reference range as well as values defined as clinically relevant will be summarized. Treatment groups will be compared descriptively with regard to distribution parameters as well as with regard to frequency and percentage of patients with abnormal values or clinically relevant abnormal values.

Vital signs, physical examinations, or other safety-relevant data observed at screening, baseline, during the course of the trial and at the end-of-trial evaluation will be assessed with regard to possible changes compared to findings before start of treatment.

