#### 7.5 DETERMINATION OF SAMPLE SIZE

Sample size is estimated assuming a maximum standardized effect size of 0.32, which is based on a mean difference between placebo and BI 1358894 of 3.0 and standard deviation of 9.5 for the primary endpoint, a one-sided alpha of 0.10, a treatment allocation ratio of 2.5:1:1:1:2 (placebo, BI 5mg, BI 25mg, BI 75mg, BI 125mg, respectively) and the pre-specified models listed in section [7.2.2.1](#). Information on the change from baseline and its standard deviation is limited since there is no BoPD approved drug. BoPD is a symptomatic and clinically heterogeneous condition and in clinical studies a high discontinuation rate has been observed. Consequently, sample size assumptions are based on expert opinion, previous BoPD research and a quetiapine pivotal trial ([R19-1108](#), [R19-1645](#), [P11-04859](#)).

For the PoC analysis of the BI 1358894 dose groups and placebo using MCPMod approach with the parameters as listed in section [7.2.2](#), a sample size of 285 (95:38:38:38:76) evaluable patients are needed to establish PoC with about 81% average power (one-sided 10% alpha level). The powers for each model shape under different assumptions are summarized in the table below.

Assuming a 20% dropout rate is considered reasonable based on unique characteristics of this population. Therefore, a total sample size of approximately 355 randomized patients are needed for this phase II trial:

- 119 patients in placebo arm
- 47 patients in each of the three lowest BI 1358894 arms
- 95 patients in the highest BI 1358894 arm

The calculations for the PoC step have been performed using DoseFinding R-package ([R15-2001](#)). The R codes for the sample size calculations as well as the analyses using the MCPMod approach will be provided in the TSAP. The family-wise type I error rate at one sided  $\alpha = 10\%$  is controlled in the sample size calculations and the analyses.

Table 7.5: 1 Power of MCPMod for each candidate set model and average power for change from baseline in ZAN-BPD at Week 10

Model	Assumption A	Assumption B	Assumption C
Maximum effect size	0.32 (Mean=3, SD=9.5)	0.35 (Mean=3.3, SD=9.5)	0.38 (Mean=3.6, SD=9.5)
Linear	81.9%	86.7%	91.6%
E max 1	81.7%	87.7%	91.6%
E max 2	75.2%	82.7%	86.6%
Sigmax	85.4%	89.1%	93.7%
Exponential	81.0%	85.8%	90.5%
Average	81.1%	86.4%	90.8%

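### SAP 7.8.4 plans no separate by-arm summary or listing for about 1,420 scheduled, centrally re-read post-baseline ECGs, which conflicts with the protocol and is not declared as a change

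*SAP*

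**What the plan says.** **Collection.** The protocol Flow Chart schedules a 12-lead ECG at Visits 1, 2, 3, 5, 7 and 9/EoT, and at eEoT for patients who stop early. The scheduled post-baseline visits are Weeks 1, 4, 8 and 12. Protocol 5.2.4 says "At time points indicated in the Flow Chart, single ECGs will be recorded" and continues: "All ECGs will be transmitted electronically to the central ECG vendor in order to enable a centralized and independent re-evaluation of all 12-lead ECGs". The vendor's report goes to the site, and decisions on findings rest with the investigator.

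**Analysis.** SAP 7.8.4 treats ECG findings as baseline conditions, or as AEs when the investigator considers them clinically relevant, and analyses them in that form. It ends: "No separate listing or analysis of these ECG data will be prepared". SAP 7.8.2 and 7.8.3, by contrast, plan descriptive analyses of laboratory data and vital signs.

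**Passages that point the other way.**
- Protocol 7.2.1 has all data listed and summarised by treatment group.
- Protocol 7.2.5 says that vital signs, physical examinations and "other safety-relevant data observed at screening, baseline, during the course of the trial and at the end-of-trial evaluation will be assessed" for changes from findings before treatment. SAP 7.8 defers to this section.
- SAP 7 says individual values of all subjects will be listed by dose group, subject and visit.
- SAP section 4, which lists changes from the protocol, does not mention ECG.

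**Use of safety.** Protocol 7.2.2.1 says safety will count in choosing the target dose.

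**The concern.** The trial's main objective is proof of concept and dose-ranging data to support dose selection for pivotal studies. For ECG, the only planned route into the report is a yes/no judgement by an investigator on each tracing. That route can pick up marked abnormalities. It is poorly suited to a small average change in an interval that grows with dose while single tracings stay unremarkable. Showing such a pattern needs a summary of values and changes by arm, and 7.8.4 plans none.

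What is at stake is part of the evidence for choosing between doses. The primary efficacy inference is not affected. The documents also leave the programmer with two instructions: general clauses that call for listing and summarising everything, and a specific sentence that says not to do so for ECG. The specific sentence is the one likely to be followed.

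**Working it through.** **1. The plan's own numbers.** Protocol 7.5 states "a sample size of 285 (95:38:38:38:76) evaluable patients are needed to establish PoC with about 81% average power", assumes 20% dropout, and concludes that "a total sample size of approximately 355 randomized patients are needed for this phase II trial".
- Total: 285 / 0.80 = 356.25.
- By arm: 95/0.8 = 118.75, 38/0.8 = 47.5 (three arms), 76/0.8 = 95.
- Planned: 119, 47, 47, 47, 95, which sum to 355. The planned total reproduces apart from rounding.

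**2. Number of post-baseline ECGs.** Count = scheduled post-baseline visits x patients.
- All randomised: 4 x 355 = 1,420 (476, 188, 188, 188 and 380 by arm).
- Only the 285 evaluable patients giving all four: 4 x 285 = 1,140, before any eEoT or partial data from dropouts.

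**3. Precision of a by-arm comparison.** The documents give no SD for change in an ECG interval, so 12 to 20 ms is an assumption. SE = SD x sqrt(1/n1 + 1/n2); the two-sided 90% half-width is 1.645 x SE.

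| Comparison with placebo | sqrt term | Half-width, SD 12 | SD 15 | SD 20 |
|---|---|---|---|---|
| 125 mg, randomised (95 v 119) | 0.1376 | 2.7 ms | 3.4 ms | 4.5 ms |
| 125 mg, evaluable (76 v 95) | 0.1539 | 3.0 ms | 3.8 ms | 5.1 ms |
| One lower dose, randomised (47 v 119) | 0.1723 | 3.4 ms | 4.3 ms | 5.7 ms |

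Worked example: SD 20, 76 v 95: SE = 20 x 0.1539 = 3.08 ms; 1.645 x 3.08 = 5.1 ms.

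**4. What could be seen.** For 125 mg versus placebo with evaluable numbers, a two-sided 5% test would have these powers (for scale only; no test is proposed):
- 10 ms shift: 99% at SD 15 and 90% at SD 20.
- 5 ms shift: 58% at SD 15 and 37% at SD 20.

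**5. Fate of a sub-threshold shift under the SAP.** The tracing is recorded and re-read centrally, and the report goes to the site. If the investigator does not judge it clinically relevant, no AE is recorded. The AE tables in SAP 7.8.1 then contain nothing from it, and 7.8.4 plans no other output. The general clauses in protocol 7.2.1 and 7.2.5 and SAP 7 would require a display, but 7.8.4 contradicts them.

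**The case against.** The strongest case is that 7.8.4 implements the stated safety endpoint. Protocol 2.2.3 and SAP 5.3 define that endpoint as the percentage of patients with (S)AEs, including clinically relevant ECG abnormalities, and AEs are tabulated by treatment. The central report goes to the site, so the investigator's judgement can draw on an independent reading. Protocol 7.2.5 does not name ECG in its sentence on change from before treatment; ECG enters only as other safety-relevant data. A DMC also reviews safety during the trial. All of this stands, and it means marked dose-related abnormalities could still show. None of it supplies a by-arm display of interval values in the final report.

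Three stronger readings are tempting and are not supported:
- *That the SAP bars all ECG analysis.* The sentence bars a separate listing or analysis. Its reference is also unclear, because the sentence before it opens with findings before first intake of trial drug. If it covers only those, 7.8.4 specifies no summary of the post-dose ECGs; if it covers all ECGs, it excludes one. Either way the text needs correction.
- *That a dose-related QTcF shift cannot be seen.* The general listing and summary clauses, if followed, would show it. The finding is an unreconciled conflict and a missing planned display.
- *That QTcF values are already with the sponsor.* In the visible text QTcF appears only in the abbreviation list. Protocol 5.2.3 says the central laboratory transfers results to the sponsor; the visible part of 5.2.4 mentions only a report to the site. Parts of both documents are not visible, so this must be checked rather than assumed.

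Two limits on yield also stand. ECGs are single recordings. They are also taken before laboratory sampling, which precedes dosing at Weeks 4 and 8, and the Week 12 visit falls the day after the last dose. Those tracings are therefore likely to be near trough, and a summary would say little about peak exposure.

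**Conclusion.** The concern holds in this form: SAP 7.8.4 plans no separate by-arm summary or listing of ECG data for about 1,420 scheduled post-baseline tracings (about 1,140 on evaluable numbers). It conflicts with protocol 7.2.1, protocol 7.2.5 and SAP 7, and SAP section 4 does not declare the departure. A graded shift below the investigator's threshold has no planned display in a trial whose dose selection is to consider safety.

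The counts follow from the documents. The precision rests on an assumed SD of change of 12 to 20 ms: the 90% half-width for 125 mg versus placebo is 2.7 to 4.5 ms with all randomised patients and 3.0 to 5.1 ms with 76 versus 95. On that basis a 10 ms shift would be visible and a 5 ms shift might not be. The visible documents do not show whether the drug affects any ECG interval, and nothing here suggests that it does. The change is worth making because it is cheap and removes a contradiction.

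**What to change.** Replace the last sentence of SAP 7.8.4 with a descriptive plan on the treated set:
- the centrally read ECG intervals by visit and arm, as value and change from baseline, with the ECG baseline stated as the last pre-dose tracing;
- an outlier table by arm, with cut-offs chosen by the sponsor and fixed before unblinding;
- a listing of flagged patients.

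Keep the AE route for clinically relevant findings, and say plainly which ECGs each sentence covers. No hypothesis test is needed.

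First confirm that the ECG vendor transfers the interval values to the sponsor. If they are not available, or the sponsor prefers to omit the summary, declare and justify that in SAP section 4 so that it no longer conflicts silently with protocol 7.2.1 and 7.2.5.

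The cost is modest programming for the summary, outlier table and listing, plus a data-transfer check. Patients undergo no extra procedures, and sample size and primary analysis are unchanged.
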